APPENDIX E: CLINICAL SAFETY MONITORING PLAN

Throughout the study, all treatment-emergent adverse events, clinical assessments, and clinical laboratory parameters will be closely monitored against the criteria for drug-induced liver injury and muscle toxicity as detailed in this Clinical Safety Monitoring Plan.

DRUG-INDUCED LIVER INJURY MONITORING

Drug-induced liver injury monitoring in patients with normal liver transaminases and bilirubin at baseline should be performed throughout the study according to the procedures summarized in the below diagram and text.

**In case of questions or if unclear how to proceed, seek advice from Medical Monitor*

AESI = adverse event of special interest; ALT = alanine aminotransferase; AST = aspartate aminotransferase; DSMC = Data Safety Monitoring Committee; INR = international normalized ratio; TBL = total bilirubin; ULN = upper limit of normal.

1. Patients with normal liver transaminases and bilirubin at baseline.
- If patients with normal baseline liver indices develop elevations of aspartate aminotransferase (AST) or alanine aminotransferase (ALT) $>2 \times$ upper limit of normal (ULN) or total bilirubin (TBL) $>1.5 \times$ ULN values during the study, repeat testing should be performed within 48 hours.
 - If there are persistent elevations (ALT or AST $>2 \times$ ULN or TBL $>1.5 \times$ ULN) upon repeat testing, close observation (testing and physical examination 2 to 3 times per week) should be implemented. The Investigator will assess and record these events on an adverse event of special interest (AESI) form and send it to the ENYO safety designee via fax or email within 24 hours.
- Study drug should be discontinued, and the patient should be followed until resolution of signs or symptoms, in the following situations:
 - ALT or AST $>8 \times$ ULN.
 - ALT or AST $>5 \times$ ULN for more than 2 weeks.
 - ALT or AST $>3 \times$ ULN and (TBL $>2 \times$ ULN or international normalized ratio [INR] >1.5).
 - ALT or AST $>3 \times$ ULN with the appearance of fatigue, nausea, vomiting, right upper quadrant pain or tenderness, fever, rash, and/or eosinophilia ($>5\%$).

For any patients who present with a constellation of syndromes indicative of liver disease as per the Investigator's overall assessment (ie, fatigue, nausea, vomiting, right upper quadrant pain or tenderness, fever, rash, and/or eosinophilia [$>5\%$]), perform liver function tests to determine if liver disease is worsening.

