3.1.4 Analysis Visits

Refer to SAP V1.0 for Part A analysis visits.

Part B

For LFC, cT1, LSM and CAP, analysis visits will be assigned according to the labelled visit. I.e. "Baseline" analysis visit will be sourced from the "Screening" visit, and "Week 12/ET" analysis visit will be sourced from the "Week 12" or "ET" visit. Note that the ET assessment will be performed only for patients on study drug for ≥4 weeks.

For all other efficacy assessments with regular scheduled visits, analysis visits will be assigned according to the labelled visit. In addition to maximize the data available for assessments with regular scheduled visits, where possible, results from ET and unscheduled visits will be allocated to a post-baseline scheduled visit according to the following rules and visit windows

described in the table below (defined as the halfway point between the target visit days). If a valid value exists for the scheduled visit to which the ET/unscheduled visit has been allocated then the value from the scheduled visit will be used in the analysis, otherwise the values from the ET/unscheduled visits will be used in the analysis for the particular scheduled visit. If there is more than one assessment within a visit window, then the analysis visit will be assigned by the following priorities:

1. Use the assessment from the visit with the matching visit label.
2. Use the visit closest to the target visit day; in the case of ties, use the earlier visit.

Analysis Visit and Target Analysis Day	Visit Windows (Analysis Days)		
	Group I	Group II	Group III
Baseline	See Section 3.1.3		
Day 14 (Week 2)	2 – 21	2 – 21	
Day 28 (Week 4)	22 – 35	22 – 42	2 – 42
Day 42 (Week 6)	36 – 49		
Day 56 (Week 8)	50 – 61	43 – 70	43 – 77
Day 70 (Week 10)	62 – 77		
Day 84 (Week 12)	78 – 91	71 – 91	
Day 98 (Week 14) EOS FUP	92+	92+	92+
Group I: ALT, AST, AST/ALT Ratio, ALP, Total Bilirubin, Gamma-glutamyltransferase (GGT)			
Group II: hs-CRP, CK, BMI, Waist Circumference, Body Weight, Waist to Height Ratio, Waist to Hip Ratio, and lipids and metabolic profile			
Group III: HbA1c and all other biomarkers of liver fibrosis and inflammation			

Note that parameters that are considered both efficacy and safety (ALT, AST, CK) will use analysis visit windowing for both the efficacy and safety summaries and analyses for Part A and Part B.

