3.7.3 Clinical Laboratory Tests

Serum chemistry, hematology, coagulation, lipid and metabolic profile parameters and urinalysis will be collected at the Screening Visit, Days 1, 7, 14, 21, 28, 56, 84, 98, and at the ET Visit (Part A) and at the Screening Visit, Days 1, 14, 28, 42 (ALT, AST, ALP, GGT, and total bilirubin only), 56, 70 (ALT, AST, ALP, GGT, and total bilirubin only), 84, 98, and at the ET Visit (Part B).

See Protocol Appendix B for analytes in the serum chemistry panel, additional chemistry parameters, hematology, coagulation, lipid and metabolic profile, and urinalysis.

The serum chemistry and additional chemistry parameters will be summarized and listed together.

Descriptive statistics of each safety laboratory parameter will be presented for baseline values and for values and the change from baseline at each post-baseline visit.

An additional summary table will be presented for CK over time for the patients in Safety Population who were taking a statin.

Values outside the normal range will be categorized as H (high, i.e. above the normal range) or L (low, i.e. below the normal range) based on the central laboratory's normal reference range. The number and percentage of patients with values outside the normal range will be summarized by parameter for each post-baseline visit.

Shift tables will also be presented for baseline vs. maximum post-baseline values and baseline vs. minimum post-baseline values for ALT, AST, Total Bilirubin and ALP. The shift tables for ALT and AST will include the following categories:

- < lower limit of normal (LLN) or Normal;
- > upper limit of normal (ULN) to $\leq 2 \times$ ULN;
- $> 2 \times$ ULN $\leq 5 \times$ ULN;
- $> 5 \times$ ULN to $\leq 8 \times$ ULN;
- $> 8 \times$ ULN.

The shift tables for Total Bilirubin and ALP will include the following categories:

- < LLN or Normal;
- > ULN to $\leq 1.5 \times$ ULN;
- $> 1.5 \times$ ULN to $\leq 2 \times$ ULN;
- $> 2 \times$ ULN.

ALT, AST, and Total Bilirubin will be assessed using the National Cancer Institute Common Terminology Criteria for Adverse Events (CTCAE). Shift tables will be presented for baseline vs. maximum post-baseline grades. The following categories are based on CTCAE Version 5.0 grading system:

Criteria	Grade 1	Grade 2	Grade 3	Grade 4

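### Read literally, the SAP's visit windowing can leave unscheduled or early-termination ALT and AST peaks out of the Part B peak-based liver safety outputs

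*SAP*

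**What the plan says.** **Record selection (SAP 3.1.4, Part B).** ET and unscheduled results are allocated to a scheduled visit by day windows. Where a valid scheduled value exists, the text says: "then the value from the scheduled visit will be used in the analysis, otherwise the values from the ET/unscheduled visits will be used". If a window holds several assessments, the first rule is: "Use the assessment from the visit with the matching visit label". After that comes closeness to the target day, then the earlier date. The size of the value plays no part.

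The passage is written for efficacy assessments. Its closing note carries it into safety: parameters that count as both efficacy and safety, named as ALT, AST and CK, "will use analysis visit windowing for both the efficacy and safety summaries and analyses for Part A and Part B". For Part A the section says only: "Refer to SAP V1.0 for Part A analysis visits".

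**Peak-based outputs (SAP 3.7.3).** For ALT, AST, total bilirubin and ALP: "Shift tables will also be presented for baseline vs. maximum post-baseline values", with a matching table for the minimum. ALT, AST and total bilirubin also have shifts to the maximum CTCAE grade. An eDISH plot is announced in one sentence. None of these says which records feed the maximum.

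**Retesting (Protocol Appendix E).** A liver-test rise past the stated threshold leads to a repeat test within 48 hours. If the rise persists, "close observation (testing and physical examination 2 to 3 times per week) should be implemented".

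**The concern.** A one-value-per-visit rule suits by-visit summaries and a repeated-measures model. It suits a maximum poorly, because it can discard the samples taken as a result of a rise. The ALT and AST shift categories are cut at 2, 5 and 8 × ULN. Appendix E uses the same multiples for patients with a normal baseline: above 2 to trigger a repeat test, and above 5 (if sustained for more than two weeks) and above 8 among its discontinuation criteria. Tables built on those cut-points could therefore leave out results obtained because a patient had crossed one of them.

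ET results are exposed in the same way. A patient who leaves during treatment is asked back within 48 hours of the last dose (Protocol 6.5). That visit's chemistry is displaced if its window already holds a scheduled value.

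Elevation of transaminases is an AESI in Part B. A windowed maximum can equal the true peak or fall below it, but cannot exceed it, so any error understates the liver signal.

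**Working it through.** The plan gives no figure to reproduce here; the point is a data-selection rule. The check applies the rule to constructed ALT series. None of these are trial data.

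**Inputs**
- ALT ULN: 53 U/L (Protocol Appendix I).
- Windows for ALT and AST: Week 8 is Days 50–61, Week 10 is Days 62–77 (SAP 3.1.4).
- CTCAE grade with a normal baseline: above 1 to 3 × ULN is Grade 1, above 3 to 5 is Grade 2, above 5 to 20 is Grade 3 (SAP 3.7.3).
- Assumed: normal baseline, and no other scheduled value above the Day 56 value.

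**1. A retest peak in a window that has a scheduled value**

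| Day | Type | ALT (U/L) | Multiple of ULN | Window | Kept? |
|---|---|---|---|---|---|
| 56 | scheduled | 120 | 120/53 = 2.26 | Week 8 | yes |
| 59 | retest | 440 | 440/53 = 8.30 | Week 8 | no, displaced by Day 56 |
| 70 | scheduled | 100 | 100/53 = 1.89 | Week 10 | yes |

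- Maximum of windowed values: 2.26 × ULN, category above 2 to 5 × ULN, Grade 1.
- Maximum of all values: 8.30 × ULN, category above 8 × ULN, Grade 3.

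**2. A series of retests (in multiples of ULN).** Scheduled values are 2.5 on Day 56 and 2.0 on Day 70. Retests are 4.5, 6.0, 8.5 and 5.0 on Days 58, 61, 63 and 66. Days 58 and 61 fall in the Week 8 window, Days 63 and 66 in the Week 10 window, and both windows hold a scheduled value. The windowed maximum is 2.5 (Grade 1); the all-values maximum is 8.5 (Grade 3).

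**3. The same series with Day 70 missed.** Two retests now compete for the Week 10 window. Day 63 is 70 − 63 = 7 days from target and Day 66 is 70 − 66 = 4 days, so Day 66 is kept. The windowed maximum is 5.0 (Grade 2), against 8.5 (Grade 3).

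**4. When nothing is lost.** If the scheduled Day 56 value is itself the peak, at 8.5 × ULN, both methods give Grade 3. If Day 70 is missed and a Day 68 retest of 8.5 × ULN is the only result in the Week 10 window, it is used and both methods again give Grade 3.

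**Condition for loss.** The retest or ET result must exceed the values that are kept, and its window must hold either a valid scheduled value or another unscheduled value that wins on closeness to the target day.

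**Scope by analyte**

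| Analyte | Named in the 3.1.4 note | Maximum shift table | CTCAE shift |
|---|---|---|---|
| ALT, AST | yes | yes | yes |
| CK | yes | no | no |
| Total bilirubin | no (same windows as ALT and AST) | yes | yes |
| ALP | no (same windows as ALT and AST) | yes | no |

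**The case against.** The strongest reply is that the windowing rule selects a value for a particular scheduled visit, and that its stated aim is to make more data available. SAP 3.7.3 ties the descriptive statistics and out-of-range counts to each visit, but gives the maximum no visit qualifier. On that reading the maximum already runs over all results. The detailed programming specifications, a separate document under SAP section 6, may settle it. This reading is possible, but the SAP does not state it. The 3.1.4 note is the only sentence on record selection for these parameters' safety outputs; it covers summaries and analyses and makes no exception. At the least, two programmers could produce different liver tables from the same text.

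The second reply is that the event would be seen elsewhere. An abnormality retested more than once, or leading to action on study drug, is reported as an adverse event (Protocol 9.1 and 9.8). Persistent elevations go on an AESI form within 24 hours. In Part B the DSMC is notified of values twice baseline. The SAP tabulates TEAEs by maximum severity and lists all safety data. This stands, and it rules out any inference that the case goes unreported. It does not correct an understated laboratory table or plot.

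Four stronger inferences are not supported:
- **CK peaks vanish from the same outputs.** CK has no maximum-value shift table, CTCAE shift or eDISH plot. Only its by-visit summaries are affected.
- **The eDISH plot pairs a windowed ALT with an unwindowed bilirubin.** The note does not name bilirubin, but bilirubin shares the ALT and AST windows in 3.1.4. Its handling is unclear; a mismatch is not established.
- **The understatement is larger on active drug.** The Part A Grade 2 and 3 elevations arose at 100 mg BID and 400 mg QD, neither of which is a Part B arm. None arose at 200 mg QD, and one of the four Part A patients with ALT above 3 × ULN was on placebo.
- **Part A is affected in the same way.** Its windows are in SAP V1.0, which is not among the documents.

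**Conclusion.** The point holds for ALT and AST in Part B. Followed as written, SAP 3.1.4 can displace a true peak from the maximum post-baseline shift tables, the maximum CTCAE grade shifts and the eDISH plot. In the worked case the tabulated result falls from 8.3 × ULN, Grade 3, to 2.3 × ULN, Grade 1.

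A reader might infer that every retest peak is lost. That is not so: steps 1 to 3 of the working show losses and step 4 shows none. The documents give no basis for estimating how often it would happen.

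The conclusion rests on a literal reading of the 3.1.4 note and on unscheduled results being in the analysis data, which 3.1.4 itself presumes. The change should be made because a stated rule can produce a wrong safety table and the correction is nearly free.

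**What to change.** - **SAP 3.1.4:** limit the closing note on ALT, AST and CK to by-visit summaries and the MMRM analyses.
- **SAP 3.7.3:** state that the maximum and minimum post-baseline shift tables (ALT, AST, total bilirubin, ALP), the maximum CTCAE grade shifts (ALT, AST, total bilirubin) and the eDISH plot use all post-baseline results, whether scheduled, unscheduled or ET, without windowing. Naming total bilirubin here also settles its handling in the eDISH plot.

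The cost is two sentences and a record-selection flag in the programs. No new data are needed, and the by-visit summaries and efficacy models do not change.

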3.1.5 Absolute Change and Relative Change

Change (absolute) from baseline will be derived for each analysis visit as visit value minus baseline.

Percent (relative) change from baseline will be derived for each analysis visit as $[(\text{visit value} - \text{baseline})/\text{baseline}] \times 100$.

3.1.6 Summary Statistics

Categorical data will generally be summarized with counts and percentages of patients. The denominator used for the percentage calculation will be clearly defined. Continuous data will generally be summarized with descriptive statistics including n (number of non-missing values), mean, standard deviation, median, and minimum, and maximum values

3.1.7 Hypothesis Testing

Unless stated otherwise, tests will be performed at the nominal alpha one-sided level of 0.025. 95% two-sided confidence intervals (CIs) will also be reported.

In Part A as only the pooled EYP001a treatment group is being compared to placebo, no adjustments for multiplicity are required.

In Part B, to adjust the 2 tests (each EYP001a dose and placebo) for multiplicity in order to control the family-wise type I error at 0.025 one-sided, the Bonferroni method will be used.

3.1.8 *Evaluation of Site Effect*

The number of subjects at each site is expected to be too small to evaluate site effect.

3.1.9 *Handling of Dropouts and Missing Data*

In general, few missing data are expected and, unless stated otherwise, they will not be replaced.

Missing values for the primary Week 12/ET endpoint, LFC, and the key secondary endpoint, cT1, will be imputed based on the missing at random (MAR) assumption using multiple imputation as the primary analysis. A sensitivity analysis for the primary endpoint, LFC, will also be carried out whereby the missing values will be imputed using the multiple imputation with tipping point method based on the missing not at random assumption. Further details of the multiple imputation methods will be provided in the relevant sections below.

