10.2.8 Sample Size Determination

The sample size of 114 randomized patients (n = 24 patients in Part A and n = 90 in Part B [n = 30 patients per treatment group]) is based on the efficacy endpoint: absolute change in LFC as measured by MRI-PDFF from baseline to Week 12, assuming that the treatment difference between each active treatment group with placebo is at least 5.1% with a common standard deviation of 5.8%.

With a 2-sample Z-test with the power of 0.8 and an overall family-wise 1-sided alpha of 0.025 (or each active versus placebo alpha = 0.0125 after Bonferroni adjustment), 26 patients per treatment group will be needed to complete the Week 12 Visit. With the consideration of an approximately 13% dropout rate before Week 12, 30 patients will be randomized per treatment group in Part B.

A Lan-DeMets alpha spending function will be used for this group sequential design. Nonbinding O'Brien-Fleming efficacy boundaries and futility boundaries will be calculated using EAST 6.4 software. The efficacy and futility boundaries are described in [Table 6](#).

At the time of the interim analysis, if the test-statistic is equal to or less than the futility boundary, the Sponsor can decide to stop the study due to lack of efficacy.

Table 6. Efficacy and Futility Boundaries for Part B

Look	Week 8 Number of Patients	Week 12 Number of Patients	Information Fraction	Cumulative Alpha Spent	Cumulative Beta Spent	Z Efficacy Boundary	Z Futility Boundary	p-value Efficacy Boundary	p-value Futility Boundary
#1 (interim analysis)	45	23	0.25	<0.0001	0.0113	-4.7604	0.6966	<0.0001	0.7570
#2 (final analysis)	90		1	0.0125	0.1962	-2.2414	-2.2414	0.0125	0.0125

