2.2.2 Randomization and Blinding

This study follows a randomized, double-blind, placebo-controlled design. Patients in Part A will be randomized via the Interactive Response Technology (IRT) system to 1 of 4 parallel treatment groups on Day 1 in a 1:1:1:1 ratio. However, prerandomization will occur within the IRT system at least 7 days prior to randomization. Patients in Part B will be randomized via the IRT system to 1 of 3 parallel treatment groups on Day 1 in a 1:1:1 ratio. Prerandomization is not applicable in Part B.

Both EYP001a and placebo will be provided as tablets for oral administration and will be identical in appearance.

Prerandomization/randomization information will be concealed from the Investigators and the patients until the end of the study, with the exception of an emergency situation involving a patient that required unblinding of the treatment assignment.

Stratification

Randomization will be stratified by statin use (yes, no) and T2DM status (yes, no) in Part A, and by statin use (yes, no) and LFC (stratification factor with 3 categories: LFC<16%, 16%≤LFC<22%, and 22%≤LFC) in Part B at screening. Randomization can occur after eligibility check on Day -3, at the earliest, and prior to dosing on Day 1 at the latest.

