2.2.4 Sample Size Determination

The sample size of 114 randomized patients (n = 24 patients in Part A and n = 90 in Part B [n = 30 patients per treatment group]) is based on the efficacy endpoint: absolute change in LFC as measured by MRI-PDFF from baseline to Week 12, assuming that the treatment difference between each active treatment group with placebo is at least 5.1% with a common standard deviation of 5.8%.

With a 2-sample Z-test with the power of 0.8 and an overall family-wise 1-sided alpha of 0.025 (or *each.active*.*versus.placebo*.*alpha* = 0.0125 after Bonferroni adjustment), 26 patients per treatment group will be needed to complete the Week 12 Visit. With the consideration of an approximately 13% dropout rate before Week 12, 30 patients will be randomized per treatment group in Part B.

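### Part B could use Holm's step-down test instead of plain Bonferroni: more power for each dose and for both doses within the same 0.025 bound, though the present rule is valid

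*SAP*

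**What the plan says.** SAP 3.1.7 covers the Part B tests with the words "In Part B, to adjust the 2 tests (each EYP001a dose and placebo) for multiplicity", and the same sentence ends "in order to control the family-wise type I error at 0.025 one-sided, the Bonferroni method will be used". SAP 3.1.1 keeps the two doses separate. SAP 3.4.1.1 applies Bonferroni to the primary ANCOVA comparisons and reports two-sided 95% and 97.5% intervals for each dose against placebo.

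The design matches that rule. Protocol 10.2.8 works "With a 2-sample Z-test with the power of 0.8 and an overall family-wise 1-sided alpha of 0.025" and takes "each active versus placebo alpha = 0.0125 after Bonferroni adjustment". SAP 2.2.4 assumes that the difference for each dose "is at least 5.1% with a common standard deviation of 5.8"%, concludes that "26 patients per treatment group will be needed to complete the Week 12 Visit", and allows for an "approximately 13% dropout rate before Week 12, 30 patients will be randomized per treatment group in Part B". Table 6 of Protocol 10.2.8 gives group-sequential boundaries at cumulative alpha 0.0125 only; the final efficacy boundary is −2.2414.

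Neither document specifies a step-down procedure, a fixed sequence or any passing on of alpha, and neither gives a reason for single-step testing. Protocol 10.2.1.1 counts three tests where the SAP counts two. Only two agrees with 0.025/2 = 0.0125.

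**The concern.** Under Bonferroni each dose is judged at 0.0125 whatever the other dose shows. Once one null hypothesis has been rejected, only one is left that could be rejected falsely, so the full 0.025 can be spent on it. Bonferroni leaves half of that unused.

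The loss falls on the dose-level conclusions, and most heavily on a dose with a weaker effect. Protocol 5.2 carries 200 mg QD forward and adds a lower dose, 100 mg QD, which was not a Part A group. Protocol 1.2.2 says that the Part A fat reduction was driven by the 200 mg and 400 mg QD doses. A smaller effect at 100 mg QD is therefore conceivable, although the sample-size text assumes at least 5.1 for both doses.

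**Working it through.** **Inputs.** Difference δ = 5.1, SD σ = 5.8 and 26 completers per group (SAP 2.2.4); per-comparison alpha 0.0125 one-sided and power 0.8 (Protocol 10.2.8); allocation to "1 of 3 parallel treatment groups on Day 1 in a 1:1:1 ratio" (SAP 2.2.2). With equal groups and a shared placebo, the two test statistics correlate at 0.5.

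**1. The plan's own figure.** n = 2[σ(z₀.₉₈₇₅ + z₀.₈)/δ]² = 2[5.8 × (2.2414 + 0.8416)/5.1]² = 24.59, so 25 per group. The two-sample t version gives power 0.784 at 25 and 0.802 at 26, which is exactly the stated 26. Dropout: 26/(1 − 0.13) = 29.9, so 30. The figure reproduces.

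**2. Bonferroni at 26 per group, both doses at 5.1.** SE = 5.8 × √(2/26) = 1.6086, so each statistic has mean 5.1/1.6086 = 3.170.
- Per dose: Φ(3.170 − 2.2414) = 0.8236 (0.82355 before rounding).
- Both doses (bivariate normal, correlation 0.5, both beyond 2.2414): 0.7199.
- At least one: 2 × 0.82355 − 0.7199 = 0.9272.

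**3. Holm, same setting.** Let J be the probability that one named dose passes 1.960 and the other passes 2.2414; J = 0.7628.
- Per dose: 0.82355 + 0.7628 − 0.7199 = 0.8665.
- Both doses: 2 × 0.7628 − 0.7199 = 0.8057.
- At least one: 0.9272, because the first step is the Bonferroni step.

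**4. Unequal effects (assumed).** The stronger dose stays at 5.1. The 80% and 60% cases are illustrations, not figures from the documents.

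| Weaker dose | Its power, Bonferroni | Its power, Holm |
|---|---|---|
| 80% of effect (4.08) | 61.6% | 69.7% |
| 60% of effect (3.06) | 36.7% | 46.4% |

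**5. Family-wise error.**

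| Truth | Bonferroni | Holm |
|---|---|---|
| Both doses null | 0.0232 | 0.0232 |
| One null, other at 5.1 | 0.0125 | 0.0249 |

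The bound of 0.025 holds throughout. Holm guarantees it under any correlation.

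**6. Robustness.** A 400,000-run simulation with t-tests at 26 per group gives 81.0% to 85.5% per dose and 70.2% to 79.4% for both. At 30 per group (no dropout) the normal calculation gives 87.8% to 91.3% and 79.9% to 86.8%.

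**7. Boundary for the second step.** Lan-DeMets O'Brien-Fleming spending at information 0.25 and one-sided 0.025 gives |Z| of about 4.33 at the interim and 1.960 at the final look. As a check, the same calculation at 0.0125 gives 4.86 and 2.2414, against 4.7604 and 2.2414 in Table 6. The final values agree; the interim values differ slightly, and the alpha involved is negligible (below 0.0001 either way).

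**The case against.** The case for leaving the plan alone is a good one. Bonferroni is valid and prespecified, and it is the rule the trial was sized for. No section sets a target for showing both doses, and the chance of at least one significant dose does not move. The two-sided 97.5% intervals match Bonferroni decisions exactly; Holm breaks that match whenever it adds a rejection, and keeping interval and decision aligned is a legitimate preference in a two-dose Phase 2a trial. SAP 4.1 records that the Part B interim was completed in February 2021, so a less conservative rule would arrive after an unblinded committee review. The calculation also uses completers and a Z-test, whereas the primary analysis is a baseline-adjusted ANCOVA on the ITT population with multiple imputation.

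All of this stands, and it is why the point is an improvement only. It does not remove the gain. The documents give no reason for single-step testing, and Holm uses no interim result. Protocol 10.2.6 has the committee's conclusions shared blindly with the sponsor. The timing has to be documented, but it does not rule the change out while the data remain unlocked and blinded.

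A reader might infer more than the documents support:
- That the plan is underpowered or fails to control type I error. It is neither; the stated 26 reproduces.
- That Holm makes a positive trial more likely. The probability of at least one rejection is identical.
- That the two methods have the same actual error. They share the bound; when one dose is null and the other works, Holm's error is about twice Bonferroni's.
- That the protocol's count of three makes the Part B level 0.025/3 = 0.0083. The sample-size text and the SAP both use two tests. The count does matter for the edit, because Holm over three tests would start at 0.0083, where first-step power per dose is 78%.

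**Conclusion.** The point holds as a low-cost efficiency gain. Under the planning assumptions Holm adds about 4 points of power per dose and 9 points for showing both. It adds about 8 to 10 points for a dose whose true effect is an assumed 80% to 60% of 5.1. It adds nothing to the chance of at least one significant dose. These figures rest on 26 completers per group, SD 5.8, correlation 0.5 and normal test statistics, and they ignore the interim look because it spends less than 0.0001. The equal-effect gain per dose shrinks to about 3.5 points at 30 per group. The price is a higher actual error when exactly one dose works, within the 0.025 bound, and intervals that may disagree with the decision on the second dose.

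**What to change.** - In SAP 3.1.7 and 3.4.1.1 and Protocol 10.2.1.1 (and its synopsis copy), specify Holm over **two** tests for Part B: the smaller one-sided p-value at 0.0125 and, if that is rejected, the other at 0.025. Correct the protocol's count of three in the same edit; changing only the method's name would leave a first step of 0.0083.
- Keep Table 6 for the first step. Add a 0.025 row for the second step, produced with the same software and settings (about −4.33 at the interim and −1.960 at the final look, in Table 6's sign convention).
- Report Holm-adjusted p-values beside the 97.5% intervals, and state that for the second-ordered dose the interval may include zero although the test rejects.
- Record the change and its reason, state that it does not depend on interim results, and date it before the first Part B database lock and unblinding described in SAP 4.2. If that point has passed, keep Bonferroni as the confirmatory rule.

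The cost is wording in both documents and one added boundary row. No patients, visits or first-step boundaries change. If the sponsor prefers intervals that always match the decision, one sentence giving that reason for keeping Bonferroni would settle the point.
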